
Safety
 
 • To describe the safety profile in each group after each and any vaccination 	
The safety profile will be evaluated for each vaccine within 30 days (+14 days) after each vaccination. The following endpoints will be used for the evaluation of safety:
 
 • Unsolicited systemic AEs reported in the

Objectives	Endpoints
	
30 minutes after each vaccination
 
 Solicited (pre-listed in the participant's diary card and [electronic] Case Report Form [CRF]) injection site and systemic reactions starting any time from the day of vaccination through 7 days after each vaccination Unsolicited (recorded in a diary card) non-serious AEs reported up to 30 days after each vaccination Serious adverse events (SAEs) (including adverse events of special interest [AESI]) reported throughout the study, ie, from D01 (first vaccination) to the last study day (D61 for Groups 1 and 2 and D31 for Group 3) 
Depending on the items, the endpoints recorded or derived could include:
 
 Nature (Medical Dictionary for Regulatory Activities [MedDRA] preferred term), time of onset, duration/number of days of presence, intensity, relationship to the vaccine, whether the AE led to early termination from the study, outcome, and seriousness criterion

Observational
 
Immunogenicity
 
 To describe the antibody response of meningococcal serogroups A, C, W, and Y measured by serum bactericidal assay using baby rabbit complement (rSBA), before and on D31 following meningococcal vaccination, in a subset of the first 50 participants from each group 	
 Antibody titers against meningococcal serogroups A, C, W, and Y measured by rSBA in a subset of the first 50 participants in each group assessed before vaccination (D01), and at D31 (+14 days): 
 $\geq 1:8$ and $\geq 1:128$ ≥ 4-fold rise from pre-vaccination to post-vaccination Vaccine seroresponse measured by rSBA in each group, with seroresponse defined as follows: 
 For a participant with pre-vaccination

Objectives	Endpoints
	
titers < 1:8, a post-vaccination titer \geq 1:32
 
 For participants with pre-vaccination titer \geq 1:8, a post-vaccination titer at least 4-fold greater than the pre-vaccination titer

 To describe the kinetics of antibody titers against meningococcal serogroups A, C, W, and Y in a subset of the first 60 participants in Group 3, measured by hSBA before, on D07, and on D31 following vaccination 	
 Antibody titers against meningococcal serogroups A, C, W, and Y measured by hSBA in a subset of the first 60 participants in Group 3 before vaccination (D01), at D07, and at D31 (+14 days) The specific endpoints will be similar to those defined for the first secondary objective at the time points applicable for the subset of Group 3

3 Statistical Considerations

3.1 Statistical Hypotheses

Primary Objective

See Section 9.1 of the protocol.

Secondary and Observational Objectives

Immunogenicity:

See Section 9.1 of the protocol.

Safety:

No hypotheses will be tested. The analyses will be descriptive.

3.2 Sample Size Determination

Approximately 464 participants are expected to be enrolled.

For the Primary Objective

With 174 enrolled participants in Group 1 and Group 2 each, the study will have a > 90% power (Farrington and Manning formula) to declare the non-inferiority of Group 1 versus Group 2 based on A, C, W, and Y hSBA antibody titers $\geq 1:8$ (difference in the percentage of seroprotected participants in the 2 groups) after a single dose of MenACYW conjugate vaccine or Nimenrix®, assuming:

- A 10% dropout rate from the PPAS (155 participants evaluable per Group 1 and Group 2)
- A 1-sided alpha level of 2.5%
- A non-inferiority margin of 10% (percentage difference)

See [Table 3.1](#) below for power of the study for primary objective.

Table 3.1: Power of the study for the primary objective

Antigen	Estimated percentage of hSBA titer $\geq 1:8$ MenACYW*	Non-inferiority margin†	Power
A	93.5%	10%	90.7%
C	98.5%	10%	> 99.9%
Y	97.2%	10%	99.3%
W	99.1%	10%	> 99.9%
Overall			$\geq 90\%$

Since the hypothesis needs to be met for all serogroups, no alpha adjustment for multiple comparisons is necessary in these calculations.

* Percentages of participants with an hSBA titer $\geq 1:8$ are based on the MET50 MenACYW (Group 1) post-dose result. The power is calculated with the assumption that the estimates from Group 1 equal that of Group 2 corresponding to the estimated percentages in Group 2 described above.

† A non-inferiority margin of 10% has been widely used in previous studies evaluating the same antigens and in a competitor's study of the same type. Also, considering the level of the reference rate taken in Group 2, it is reasonable to use 10%.

For the Secondary and Observational Objectives

The sample size has been arbitrarily set to 116 participants in Group 3, as well as the sample size of the subsets, as these data are not intended to be used for any hypothesis testing. No formal sample size calculations were performed.

In case of unexpected situations or any study hold resulting in an unexpected number of unevaluable participants, total sample size may be increased to replace withdrawn, or unevaluable participants.

3.3 Populations for Analyses

The following populations are defined:

Population	Description

Safety Analysis Set (SafAS)
	
Participants who have received at least one dose of the study vaccines¹ and have any safety data available
 
Three SafAS will be defined.
 
Overall SafAS for any dose:
 
Participants who have received at least one dose of the study vaccines² and have any safety data available
 
SafAS for vaccination at Visit 1 (SafAS1):
 
Participants who have received at least one dose of the study vaccines^a at Visit 1 (all groups) and have any safety data available.
 
SafAS for vaccination at Visit 2 (SafAS2):
 
Participants who have received at least one dose of the study

¹ For which safety data are scheduled to be collected.

² For which safety data are scheduled to be collected.

Population	Description
	vaccines ^a at Visit 2 (Group 1 and 2) and have any safety data available. For each SafAS, all participants will have their safety analyzed according to the study vaccine they actually received. Safety data recorded for a vaccine received out of the protocol design will be excluded from the analysis (and listed separately).
Full analysis set (FAS)	Not applicable for SMT analysis
Per-protocol analysis sets (PPAS)	Not applicable for SMT analysis

The safety analysis will be performed on the Safety Analysis Set (SafAS, SafAS1 and SafAS2).

3.4 Statistical Analyses

This section is a summary of the planned statistical analyses of all safety endpoints.

3.4.1 General Considerations

The statistical analyses will be performed under the responsibility of the Sponsor's Biostatistics platform using SAS® Version 9.4 or later.

For descriptive purposes, the following statistics will be presented:

Table 3.2: Descriptive statistics produced

Disposition and follow-up description	Categorical data	Number of subjects. Percentage of subjects.
	Continuous data	Mean, standard deviation, quartiles, minimum and maximum.
Baseline characteristics	Categorical data	Number of subjects. Percentage of subjects.
	Continuous data	Mean, standard deviation, quartiles, minimum and maximum.
Clinical safety results	Categorical data	Solicited: Number and percentage (95% CIs for main endpoints) of subjects. Unsolicited: Number and percentage (95% CIs for main endpoints) of subjects and number of events.

The confidence interval (CI) for the single proportion will be calculated using the exact binomial method (Clopper-Pearson method, quoted by Newcombe (1), i.e., using the inverse of the beta integral with SAS®).

3.4.2 Primary Endpoint

Not applicable for SMT analysis.

3.4.3 Secondary Endpoints***Immunogenicity***

Not applicable for SMT analysis.

Safety

Safety results will be described for participants in all study groups. Group 1 and Group 2 will be pooled in order to maintain the blind. The main parameters for the safety endpoints will be described by frequency counts and 95% CIs (based on the Clopper-Pearson method).

Safety analyses will include but are not limited to the following descriptions listed in [Table 3.3](#)

Table 3.3: Statistical analyses for safety secondary objectives

Item	Time and Group	Description
All and related Immediate unsolicited systemic AEs	Within 30 minutes after each vaccination; Within 30 minutes after any vaccine injection	Summary Frequency Table presenting the number and percentage of subjects experiencing the endpoint of interest as well as the number of AEs/ARs by MedDRA SOC and PT.
All and related AEs leading to study discontinuation	D0 to D30 after each vaccination; During the entire study period after any vaccination (i.e. from Day 0 to last phone call)	Summary Frequency Table presenting the number and percentage of subjects experiencing the endpoint of interest as well as the number of AEs/ARs by MedDRA SOC and PT.
Solicited reactions	D0 to D7 after each vaccination D0 to D7 after any vaccination.	Summary Frequency Table presenting the number and percentage of subjects experiencing the endpoint of interest for solicited injection site reaction and solicited systemic reaction during the solicited time period.
All and related Unsolicited	D0 to D30 after each vaccination;	Summary Frequency Table presenting the number and percentage of subjects

Item	Time and Group	Description
non-serious AEs	D0 to D30 after any vaccination	experiencing the endpoint of interest as well as the number of all AEs/ARs by MedDRA SOC and PT.
AEs ongoing	At D30 after each vaccination; At D30 after any vaccination	Summary Frequency Table presenting in a blinded manner the number and percentage of subjects experiencing the endpoint of interest as well as the number of AEs/ARs by MedDRA SOC and PT
All and related SAEs	Day 0 to Day 30 after each vaccination;	Summary Frequency Table the number of subjects experiencing the endpoint of interest as well as the number of SAEs by MedDRA SOC and PT
All and related AESIs	During the entire study period after any vaccination	Summary Frequency Table the number of subjects experiencing the endpoint of interest as well as the number of AESIs by MedDRA SOC and PT

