# 9 Statistical Considerations

Clinical data will be analyzed under the responsibility of the Biostatistics Platform of the Sponsor. A Statistical Analysis Plan (SAP) will be written and peer-reviewed before any analyses. In accordance with the protocol, the SAP will describe all analyses to be performed by the Sponsor and all the conventions to be taken.

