## 9.4 Statistical Analyses

The SAP will be finalized prior to database lock and it will include a more technical and detailed description of the statistical analyses described in this section. This section is a summary of the planned statistical analyses of all the endpoints including primary, secondary, and observational endpoints.

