##### *Safety*

For secondary safety endpoints, refer to [Section 3](#).

Safety results will be described for participants in all study groups. The main parameters for the safety endpoints will be described by frequency counts and 95% CIs (based on the Clopper-Pearson method).

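### Does pooling Groups 1 and 2 in the SAP's safety tables leave the per-group safety objective unanswered?

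*SAP*

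**What the plan says.** The safety objective in SAP Table 2.1 is "To describe the safety profile in each group after each and any vaccination"; protocol Table 3.1 words it identically. Protocol 9.4.3 (Safety) states that "Safety results will be described for participants in all study groups" and mentions no pooling.

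SAP 3.4.3 repeats that commitment and then adds "Group 1 and Group 2 will be pooled in order to maintain the blind". The table that follows, Table 3.3, is titled "Statistical analyses for safety secondary objectives". SAP 3.4 introduces the whole section with "This section is a summary of the planned statistical analyses of all safety endpoints". SAP 3.3 says of each safety set that "all participants will have their safety analyzed according to the study vaccine they actually received".

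On timing, SAP 3.5 and protocol 9.5 agree. There is no early safety data review and no analysis ahead of the study's formal end, but an in-house safety committee watches for signals throughout.

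**The concern.** After Visit 1, Group 1 has received MenACYW and Group 2 has received Nimenrix. A single column for both describes the safety of neither, yet it sits under a title that presents it as the answer to a per-group objective. It also fits poorly with analysis by vaccine actually received.

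The rest of the text examined does not obviously repair this. It specifies no unpooled table for Group 1 or Group 2, no rerun after unblinding, and no other analysis plan. Protocol section 9 promises that "the SAP will describe all analyses to be performed by the Sponsor and all the conventions to be taken", and protocol 9.4 that "it will include a more technical and detailed description of the statistical analyses described in this section", so a reader may expect the final safety tables here. If the pooled tables were the only ones produced, two of the three groups would have no separate safety description. The loss would be greatest after Visit 1 and smaller after Visit 2, when both groups receive 9vHPV and Tdap-IPV.

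**Working it through.** **1. Size of the pooled column.** The inputs are the 464 participants and the 3:3:2 ratio (SAP Table 1.1).

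- Groups 1 and 2: 464 × 3/8 = 174 each. Group 3: 464 × 2/8 = 116. All agree with the SAP.
- Pooled column: 174 + 174 = 348, and 348/464 = 75%.

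**2. What a pooled column hides.** The documents give no safety event rates, so the counts here are assumptions. The interval is Clopper-Pearson, as the SAP specifies: lower limit = Beta quantile at 0.025 with parameters (x, n − x + 1); upper limit = Beta quantile at 0.975 with parameters (x + 1, n − x). When x = 0, the lower limit is 0 and the upper limit is 1 − 0.025^(1/n).

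| Column | x/n | % | 95% CI |
|---|---|---|---|
| Pooled | 14/348 | 4.0 | 2.2 to 6.7 |
| Even split, each group | 7/174 | 4.0 | 1.6 to 8.1 |
| Extreme split, one group | 14/174 | 8.0 | 4.5 to 13.1 |
| Extreme split, other group | 0/174 | 0 | 0 to 2.1 |

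The pooled row is compatible with either split. So the worry is sound arithmetically if, and only if, no unpooled tables are ever made.

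**3. Whether the SAP is the final safety plan.** Setting its sections side by side:

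- Section 3.3 marks the FAS and PPAS as outside the SMT analysis. Sections 3.4.2, 3.4.3 (immunogenicity), 3.4.4, 3.4.5, 4.2.3 and 4.2.4 do the same for the primary endpoint, secondary immunogenicity, observational endpoints, the COVID-19 sensitivity analysis, derived immunogenicity and efficacy.
- A plan that leaves out the trial's primary non-inferiority test cannot be the complete SAP promised in protocol 9 and 9.4. If its silence on unpooled safety tables proved that none are planned, its silence on the primary endpoint would equally prove that the primary test is unplanned. Nobody would read it that way.
- In Table 3.3, the row for ongoing adverse events says that results are shown blinded, which fits a blinded review.
- Section 5 lists no change to the planned analyses. If pooling were meant to replace the protocol's per-group description, it would belong there.

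**4. Whether pooling is right for such a review.** Protocol 6.3.2 keeps the sponsor blinded to vaccine in Groups 1 and 2 and makes Group 3 open-label. SAP 3.4.1 has the sponsor's own biostatistics group run the analyses. While the blind holds, that group cannot separate Groups 1 and 2 and can show Group 3 on its own. SAP 3.4.3 does exactly this.

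**5. Effect on design figures.** The power table concerns hSBA titers in Groups 1 and 2. Safety is descriptive and tests no hypothesis, so moving from one column of 348 to two of 174 changes neither sample size nor power.

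**The case for a change.** The best case for a change rests on the SAP's own words. It never defines SMT, not even in its abbreviation list. It claims to cover all safety endpoints, and it labels the pooled tables as the analysis of the safety objectives. The open-ended introduction to Table 3.3 allows further tables but names none. The reason for pooling is also left hanging: if the tables are run at study end, it is unclear why the blind still needs protecting; if earlier, SAP 3.5 and protocol 9.5 seem to rule them out. A few sentences would settle all this at no cost in data.

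Most of that stands as a description of loose drafting. It does not show a wrong analysis. The reference to all safety endpoints narrows the protocol's parallel sentence, which covers primary, secondary and observational endpoints, so it points towards restricted scope. On timing, the ongoing internal monitoring allowed in both documents gives a blinded tabulation a natural place. The SAP's front pages, where scope is normally stated, were not in the text examined, so a scope statement or cross-reference there cannot be excluded.

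**Conclusion.** The concern does not hold as a defect in the analysis. Pooling is proper for a blinded sponsor-run safety review, and the protocol's commitment to describe every study group remains in force. The gap is one of missing detail: SMT is undefined, the tables carry a broader title than their purpose, the text examined has no pointer to the unblinded tables, and the timing is not spelled out. A sponsor's statistician would fill it by running the same Table 3.3 outputs for Groups 1, 2 and 3 separately once the blind is broken, as the objective and protocol 9.4.3 require. Writing that down would not alter those results.

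The pooled column holds 348 of 464 participants (75%), but the effect on power, on the primary endpoint and on the final per-group tables is nil.

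This rests on two assumptions: that the SMT analysis is a blinded safety review, which the text strongly suggests but does not state, and that the final analysis follows protocol 9.4.3. No plan for that final analysis was available, so its content can be neither confirmed nor denied. Evidence that the final report would itself show Groups 1 and 2 only in combination would reopen the point.

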Group 1: MenACYW conjugate vaccine on D01 + 9vHPV on D31 + Tdap-IPV on D31

Group 2: Nimenrix® on D01 + 9vHPV on D31 + Tdap-IPV on D31

Group 3: MenACYW conjugate vaccine + 9vHPV + Tdap-IPV on D01

The schedule of activities for Group 1 and Group 2 are given in [Table 1.2](#) and for Group 3 are given in [Table 1.3](#).

Table 1.2: Schedule of activities for Group 1 and Group 2**Phase IIIb Study, 3 Visits, 2 Vaccination Visits, 2 Telephone Calls, 3 Vaccine Injections, 3 Blood Collections, 60 Days Duration Per Participant**

Visit/Contact	Collection of information in the CRF	Visit 1	TC 1	Visit 2	TC2	Visit 3
Study timelines (days)		Day 01	Day 09 (Visit 1 + 8 days)	Day 31 (Visit 1 + 30 days)	Day 39 (Visit 2 + 8 days)	Day 61 (Visit 2 + 30 days)
Time windows (days)			+2 days	+14 days	+2 days	+14 days
Visit procedures:						
ICF and AF	X	X				
Inclusion/exclusion criteria	X	X				
Collection of demographic data	X	X				
Urine pregnancy test (if applicable)		X		X		
Collection of medical history	X	X				
Physical examination (including temperature)*		X		X		X
Contact IRT system for participant number allocation and vaccine dose randomization	X	X				
Review of temporary contraindications for blood sampling†		X		X		X
Blood sampling		BL01AA or BL01AR ¥ (5 mL)‡		BL02AA or BL02AR ¥ (8 mL)‡		BL03AA (8 mL)
Review warnings and precautions to vaccination		X		X		
Review of contraindications to subsequent vaccination				X		

Visit/Contact	Collection of information in the CRF	Visit 1	TC 1	Visit 2	TC2	Visit 3
Study timelines (days)		Day 01	Day 09 (Visit 1 + 8 days)	Day 31 (Visit 1 + 30 days)	Day 39 (Visit 2 + 8 days)	Day 61 (Visit 2 + 30 days)
Time windows (days)			+2 days	+14 days	+2 days	+14 days
Visit procedures:						
Vaccination with MenACYW conjugate vaccine or Nimenrix® (IM in deltoid muscle)		X				
Vaccination with 9vHPV and Tdap-IPV vaccines (IM in deltoid muscle of contralateral arm, with the 2 injections separated by minimum 2.5 cm)				X		
Immediate surveillance (30 minutes)	X	X		X		
Diary card provided		DC1		DC2		
Telephone call			X§		X§	
Diary card reviewed and collected				DC1		DC2
Collection of solicited injection site and systemic reactions	X	X**		X***††		X††
Collection of unsolicited non-serious AEs	X		Day of vaccination to 30 days after vaccination			
Collection of SAEs, including AESI††	X		To be reported at any time during the study			
Collection of reportable concomitant medications	X	X		X		X

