Collection of pregnancies	X		To be reported at any time during the study			
End of Active Phase participation record	X					X

Abbreviations: AE: adverse event; AESI: adverse events of special interest; AF: Assent Form; BL: blood sampling; CRF: Case Report Form; DC: diary card; ICF: Informed Consent Form; IM: intramuscular; IRT: interactive response technology; SAE: serious adverse event; TC: telephone call

* Physical examination should be performed as per standard of care including, but not limited to, a general examination of the main body systems of interest (ie, heart, lung, skin, neurologic, muscular-skeletal, lymphatic

system, etc). Temperature to be measured by oral (preferred route), rectal, or axillary route using a digital thermometer before vaccination and daily during the 7 days after vaccination and recorded in the diary card. If a routine examination had been performed within the last week by the Investigator, a sub-Investigator, or a licensed nurse practitioner, it does not need to be repeated unless there were some changes in health status, in which case it may be limited to the affected area.

† Should a participant receive oral or injectable antibiotic therapy within 3 days prior to any blood draw, the Investigator will postpone that blood draw until it has been 3 days since the participant last received oral or injectable antibiotic therapy. Postponement must still be within the timeframe for blood draw. If postponement would result in the sample collection falling outside of this timeframe, the blood sample should be collected without postponement, and it should be appropriately documented that the sample was taken less than 3 days after stopping antibiotic treatment.

¥ Blood sample corresponding to the rSBA subset of participants.

‡ Blood sample at Day 01 and Day 31 will be drawn before administration of the vaccines.

§ This call is made 8 days to 10 days after the respective vaccinations. If Day 09 (+2 days) or Day 39 (+2 days) falls on a weekend or holiday, the telephone call may be made on the following business day. During this telephone call, the staff will find out whether the participant experienced any SAE (including any AESI) not yet reported, and will remind the participant's parent/legally acceptable representative to continue using the diary card, bring the diary card to the study center at the next visit, and confirm the date and time of the next visit.

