Time windows (days)			+2 days	+2 days	+14 days
Visit procedures:					
Collection of SAEs, including AESI***	X		To be reported at any time during the study		
Collection of reportable concomitant medications	X	X	X		X
Collection of pregnancies	X		To be reported at any time during the study		
End of Active Phase participation record	X				X

Abbreviations: AE: adverse event; AESI: adverse events of special interest; AF: Assent Form; BL: blood sampling; CRF: Case Report Form; DC: diary card; ICF: Informed Consent Form; IM: intramuscular; IRT: interactive response technology; SAE: serious adverse event; TC: telephone call

* Visit at Day 07 (+2 days) is applicable only for a subset of participants, N=60. This subset of participants will have 3 blood samplings. All other participants in Group 3 will have only 2 study visits and 2 blood samplings.

† For a subset of participants (N=60) who have Day 07 (+2 days) visit, TC1 discussions can occur during Day 07 visit and TC1 at Day 09 (+2 days) is therefore optional.

‡ Physical examination should be performed as per standard of care including, but not limited to, a general examination of the main body systems of interest (ie, heart, lung, skin, neurologic, muscular-skeletal, lymphatic system, etc). Temperature to be measured by oral (preferred route), rectal, or axillary route using a digital thermometer before vaccination and daily during the 7 days after vaccination and recorded in the diary card. If a routine examination had been performed within the last week by the Investigator, a sub-Investigator, or a licensed nurse practitioner, it does not need to be repeated unless there were some changes in health status, in which case it may be limited to the affected area.

§ Should a participant receive oral or injectable antibiotic therapy within 3 days prior to any blood draw, the Investigator will postpone that blood draw until it has been 3 days since the participant last received oral or injectable antibiotic therapy. Postponement must still be within the timeframe for blood draw. If postponement would result in the sample collection falling outside of this timeframe, the blood sample should be collected without postponement, and it should be appropriately documented that the sample was taken less than 3 days after stopping antibiotic treatment.

¥ Blood sample corresponding to the rSBA subset of participants.

** Blood sample at Day 01 will be drawn before administration of the vaccines.

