4.2.1.2.4 Time of Onset

Time of onset is derived from the start date of the unsolicited AE and the date of last vaccination as described in Section [4.2.1.2.3](#):

Time of Onset = start date of the unsolicited AE - date of last vaccination before the unsolicited AE + 1.

The time of onset is considered as missing only if one or both dates are missing or partially missing.

The unsolicited AEs will be analyzed “Within 30 days” after each vaccination, which corresponds to AEs with a time of onset between 1 and 31 days or missing. An AE with missing time of onset will be considered to have occurred just after the last vaccination (computed according to the Section 4.2.1.2.3), so will be included in these tables.

Time of onset period is computed as D1-D4, D5-D8, D9-D15, D16 or later, and Missing.

Note: Unsolicited AE that occurred before vaccination (negative time of onset) or with a time of onset higher than defined above will not be included in analysis but will be listed separately.

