4.2.2.6 Adverse Events Leading to Study Discontinuation

This information will be summarized as collected. A flag is available in the clinical database for all AEs in order to identify AEs leading to discontinuation before the end of active phase.

In general, the items that are counted are:

- Disposition table: A participant who, on the “Completion at End of Study” form question “What was the participant’s status?” has “Adverse Event” checked.
- Safety overview table: A participant who has either on the “Completion at End of Study” form, question “What was the participant’s status?” has “Adverse Event” checked or lists a solicited AE that has “Caused Study Termination” checked that is at least Grade 1 or an unsolicited AE that has “Caused Study Discontinuation” checked that is at least Grade 1 or missing and is within the time period indicated.
- System Organ Class (SOC)/Preferred Term (PT) table: A solicited AE that has “Caused Study Termination” checked that is at least Grade 1 or an unsolicited AE that has “Caused Study Discontinuation” checked that is at least Grade 1 or missing and is within the time period indicated.

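### SAP Table 3.3 ends the whole-study period for AEs leading to discontinuation at the last phone call, nominally 22 days before the last visit

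*SAP*

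**What the plan says.** This SAP covers the SMT safety analysis, in which Groups 1 and 2 are pooled to keep the blind (SAP 3.4.3). In its Table 3.3, the row for AEs leading to study discontinuation has two periods. One is D0 to D30 after each vaccination. The other is "During the entire study period after any vaccination (i.e. from Day 0 to last phone call").

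The following places bear on that second period:

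- **SAP Table 1.2 (Groups 1 and 2).** The footnote on TC1 and TC2 says "This call is made 8 days to 10 days after the respective vaccinations". Visit 3 is at "Day 61 (Visit 2 + 30 days"), with a window of +14 days. The "End of Active Phase participation record" is marked at Visit 3.
- **SAP Table 1.3 (Group 3).** The only call, TC1, is at Day 09 (+2 days) and Visit 3 is at Day 31 (+14 days). For the 60 participants in the D07 subset, "TC1 discussions can occur during Day 07 visit and TC1 at Day 09 (+2 days) is therefore optional".
- **SAP 4.2.2.6.** A database flag is available "in order to identify AEs leading to discontinuation before the end of active phase". The SOC/PT table, and the part of the safety overview driven by AE flags, count an unsolicited AE whose grade is at least 1 or "missing and is within the time period indicated".
- **SAP 4.2.1.2.4.** The 30-day tables use a window "which corresponds to AEs with a time of onset between 1 and 31 days or missing". AEs with later onset are only listed.

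**The concern.** A line labelled as covering the entire study should contain every event in the per-vaccination lines beside it. Here the parenthesis stops the period at a contact that comes well before the end of participation. It conflicts directly with SAP 4.2.2.6, which ties these events to the end of the active phase, recorded at Visit 3. It also differs from the AESI row of the same table, which has no phone cut-off. As context, SAP 4.2.5.2 runs a participant's time in the trial to the last visit or termination date, and protocol 4.4 defines completion by the last planned visit.

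The parenthesis also decides what is counted, because SAP 4.2.2.6 applies the stated period as a condition. An unsolicited AE leading to discontinuation, with onset after the last call and up to onset day 31, would appear in the 30-day line and be missing from the whole-study line. For the Group 3 D07 subset the stated end point may not exist at all.

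**Working it through.** **Inputs** (SAP Tables 1.2 and 1.3): Visit 2 = Visit 1 + 30 (+14) in Groups 1 and 2. Last scheduled call = last vaccination + 8 to 10 days. Visit 3 = last vaccination + 30 (+14) days, in every group.

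**1. The schedule days reproduce.** Groups 1 and 2: Visit 2 = 1 + 30 = Day 31; TC2 = 31 + 8 = Day 39; Visit 3 = 31 + 30 = Day 61. Group 3: TC1 = 1 + 8 = Day 09; Visit 3 = 1 + 30 = Day 31.

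**2. Gap from last scheduled call to Visit 3.**

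- Nominal: 61 − 39 = 22 days in Groups 1 and 2; 31 − 9 = 22 days in Group 3.
- Minimum within windows: 30 − 10 = 20 days.
- Maximum within windows: 44 − 8 = 36 days.

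A call moved past a weekend or holiday shortens the gap slightly.

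**3. Overlap with the 30-day line after the last vaccination.** SAP 4.2.1.2.4 defines onset day = start date − vaccination date + 1, so D0 to D30 is onset days 1 to 31. The day of the call is counted as inside the period.

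| Call | Onset day of call | Days in the 30-day line but after the call | Share |
|---|---|---|---|
| +8 days | 9 | 10 to 31 = 22 | 22/31 = 71.0% |
| +10 days | 11 | 12 to 31 = 20 | 20/31 = 64.5% |

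**4. First vaccination in Groups 1 and 2.** From Day 0 to TC2 is 30 + 8 = 38 to 44 + 10 = 54 days. For participants who reach TC2, the whole-study line is therefore not shorter than the 30-day line for vaccination 1.

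**5. Nominal share of Visit 1 to Visit 3 covered by the whole-study line.** Groups 1 and 2: 38/60 = 63.3%. Group 3: 8/30 = 26.7%. These are shares of scheduled time, not of events.

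**6. Solicited reactions.** Protocol 8.3.1 collects them only to D08, before the earliest scheduled call at onset day 9, so they are not affected.

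**7. Group 3 without a call.** TC1 is optional for 60 of 116 participants (60/116 = 51.7%).

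**The case against.** The strongest objection concerns the meaning of the last phone call. This row contains only participants whose AE led to discontinuation. Protocol 7.2 asks sites to contact early terminators and complete the scheduled safety follow-up, and protocol 8.3.3 requires an AE that caused discontinuation to be followed until it resolves, stabilises or becomes chronic. A call later than TC1 or TC2 is therefore plausible for exactly these participants. This stands as a limit on the size: the figures above assume scheduled calls. It does not rescue the text, because the SAP does not define the term, and that reading would give each participant a different, unspecified end date.

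It can also be said that the parenthesis is loose wording and that little is lost from reporting. Events up to onset day 31 still appear in the 30-day line, SAEs and AESIs have their own whole-study periods (SAP 4.2.1.2.7 and 4.2.1.2.8), the disposition table has no time limit, and Table 3.3 is expressly not exhaustive. All of this is right and explains the low severity. The parenthesis nevertheless remains the only stated definition of the period, and a programmer who follows it builds the wrong window.

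Finally, the note proposed under the fix might seem to overlook that protocol 8.3.1 ends SAE collection 30 days after the last vaccination. It does not conflict: when Visit 2 falls late in its window, onset days 32 to 44 after vaccination 1 are still within SAE collection.

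**Conclusion.** The concern holds, as a minor one. Read literally, the whole-study line for AEs leading to discontinuation stops 22 days before Visit 3 (20 to 36 within windows). After the last vaccination it omits 20 to 22 of the 31 onset days that the neighbouring line includes. In the SOC/PT table the whole-study count could then be lower than the per-vaccination count.

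This rests on two assumptions: that the last phone call means the last scheduled call, and that an AE is placed in a period by its onset. The documents give no rate of discontinuation AEs, so the number affected cannot be estimated. Few are expected, since Visit 3 is the only scheduled contact after the last call.

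The analysis is descriptive and offers no contrast between the two meningococcal vaccines. The disposition table, overview participants identified through the completion form, the SAE and AESI summaries, and the primary result are unaffected.

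**What to change.** 1. In SAP Table 3.3, replace the parenthesis in the whole-study period for this row with: *from the first vaccination at Visit 1 to the participant's last visit or study termination date*. This agrees with SAP 4.2.2.6, SAP 4.2.5.2 and protocol 4.4, and gives every participant a defined end date, including Group 3 participants without a call.
2. In SAP 4.2.1.2.4, state that the onset-day-31 limit, and the rule that later AEs are only listed, apply to the per-vaccination 30-day tables and not to this whole-study line. Without this, later onsets would still be excluded after the first edit. Add a note that unsolicited non-serious AEs are collected only from D01 to D31 after each vaccination (protocol 8.3.1), so from onset day 32 the line will hold mainly SAEs and AESIs.

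The cost is two sentences in the SAP and the end date of one programming window.
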